- *The expected duration for the investigators to complete the study (complete analysis)*

It is anticipated that approximately two years will be needed to complete this entire project. We expect that patients will be enrolled starting in August 2016. We anticipate recruitment to take one year and be complete by August 2017. Data entry will be ongoing during this time and should also be complete by November to December of 2017 (or 3 months after last patient is enrolled). Data analysis will be completed by February 2018. Our final goal is to submit the abstract for the AUGS 2018 fall meeting.

Timeline	August 2016- Sept 2016	Aug 2017-Dec 2017	Jan 2018-Feb 2018
Subject recruitment, surgery, through 3 month follow up			
Data analysis		↔	
Manuscript preparation			↔

7. Study Endpoints

7.1. Describe the primary and secondary study endpoints.

The **primary endpoint** of our study is to compare patient satisfaction between postoperative follow-up with clinic visits versus telephone calls in a randomized, non-inferiority controlled trial.

7.2. Describe any primary or secondary safety endpoints.

Outpatient Visits versus Telephone Interviews for Postoperative Care: A Randomized Controlled Trial (OPTIONS)

The **primary safety endpoint** of our study is to determine the difference in adverse events, emergency room visits, primary care physician visits between patients with postoperative follow-up in the clinic versus telephone calls.

Our **secondary endpoint** is to compare the patients' nonmedical costs (gas money, time from work, child care, etc) between those who follow-up postoperatively in the clinic versus telephone calls.

7.3. Describe any exploratory endpoints.

Our **exploratory endpoint** is to determine if there is a difference in pain and pelvic floor symptoms in patients with follow-up with clinic visits versus telephone calls. The pain assessment will be measured by the Surgical Pain Scales. The pelvic floor symptoms will be measured by the Pelvic Floor Disorder Inventory (PFDI-20).

8. Research Setting

8.1. Describe the sites or locations where your research team will conduct the research.

The study will be performed at the University of New Mexico Hospital (UNMH), Sandoval Regional Medical Center (SRMC), and the associated Urogynecology clinics.

8.2. Identify where your research team will identify and recruit potential subjects.

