Patients who meet inclusion criteria will be invited to participate in the study. All patients who agree will give written consent prior to their surgery. All patients will complete baseline questionnaires including the following: Surgical Pain Scales, Pelvic Floor Disorder Inventory (PFDI-20), the Preoperative S-CAHPS questionnaire, and the European Quality of Life-5 Dimensions (EQ-5D). Data collected in addition to the above outcome measures will include *Patient Demographics*: age; self-reported race and ethnicity; primary language, marital status, education, health insurance, annual income estimate, and living arrangements. Also, *Medical/Surgical History*: medical comorbidities; prior surgeries for pelvic floor disorders. The physician's physical exam will include the following: Pop-Q stage, height, weight, and pelvic floor disorder diagnoses. The *Patient Contact* form will be completed for all patients enrolled.

Day of Surgery:

On the day of the patient's surgery, the operation that was decided between the patient and her physician will be performed. Information including the indications for surgery, procedures performed, length of surgery, and any intraoperative adverse events will be collected. This information will be recorded by the surgeon immediately postoperative in the *Surgeons Report* form.

Immediately Postoperative:

The Immediately Postoperative S-CAHPS questionnaire will be completed before discharge. If the patient stays overnight in the hospital after surgery, the S-CAHPS questionnaire will be completed on postoperative day #1. For women

Outpatient Visits versus Telephone Interviews for Postoperative Care: A Randomized Controlled Trial (OPTIONS)

undergoing day surgery the form will be completed in the postoperative holding area.

Randomization:

Computer generated randomization will be assigned by research staff uninvolved with recruitment and will be stored in opaque, sequentially numbered envelopes. On the day of the patient's discharge following surgery, the Urogynecology team will call the research coordinator and the patient will be randomized to either clinic visits or telephone calls for postoperative follow-up. Both the clinic visits and telephone calls will be scheduled with specific dates and times. These intervals are at 1-2 weeks, 6 weeks (+/-2 weeks), and 3 months (+/-3 weeks) as this is our current practice. See table 1.

Patients randomized to telephone calls:

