4. Pelvic Floor Distress Inventory (PFDI-20): This is a validated, reliable and responsive 20-question form with 3 scales (Urinary Distress Inventory, Pelvic Organ Prolapse Distress Inventory, and Colorectal-Anal Distress Inventory) assessing women with pelvic floor disorders. [22]
5. Surgical Pain Scales: Four visual analog scales that measure pain at rest, pain during normal activities, pain during work or exercise, and pain unpleasantness. [23]

13. Data Analysis

Data Analysis: Between and within group differences will be evaluated using Fisher’s exact test for categorical variables and t-tests for continuous variables.

Outpatient Visits versus Telephone Interviews for Postoperative Care: A Randomized Controlled Trial (OPTIONS)

If there are any baseline differences between groups, and multivariate analysis will determine the contribution of these differences to observed differences (if any) between groups.

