Power Analysis: Our power calculation is based on our primary outcome—patient satisfaction. We have been able to identify two publications that have used the S-CAHPS; both of these reported scores for individual items, as well as composites of “top box” responses for individual items. For example, responses for the question, “After your surgery did the surgeon listen carefully to you?” has three responses: 1. Yes, definitely, 2. Yes, somewhat, and 3. No. A top box response is “Yes, definitely”. The global satisfaction with their surgeon is a single item, ranging from 0 (worst surgeon possible) to 10 (best surgeon possible), with “top” box responses of 10. “Top” box responses in prior studies ranged from 56-100% with the majority of responses about 90%. Assuming both the control and experimental groups are equivalent in patient satisfaction, a non-inferiority calculation can be applied using 90% as the percentage “success” in the control group and experimental groups with 80% power, an alpha of 0.05, and 15% non-inferiority limit. In this equation, if there is truly no difference between the control and experimental groups, then 100 patients for total sample size are required to be 80% sure that the upper limit of a 90% two-sided confidence interval will exclude a difference in favor of the control group of more than 15%. Our primary outcome measure is the global composite for the surgeon rating, which has been used in the previous studies. This sample size will provide similar power for comparison of other items and scale of the S-CAHPS between groups. We anticipate that up to 10% of women who are recruited will have complications that preclude them from participation after consent and prior to randomization, such as poorly controlled pain, complications or surgeon concerns. In addition, we anticipate that 10% of women will be lost to follow-up. Therefore we plan to recruit a total of 120 women, 60 per group. All data will be entered into REDcap and undergo data cleaning. Data analysis will be performed as instructed by the CAHPS Analysis Program using the CAHPS41.SAS macro program provided by the AHRQ. Analysis will be performed using Fisher’s Exact test for categorical variables, t-tests for continuous variables, and Wilcoxon Rank test for ordinal variables with significance set at $P<0.05$. Evaluation of potential confounders (e.g. age, baseline questionnaire) will be performed using regression methods, if, by chance there are differences between groups.

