Statistical Analysis: Differential mean costs and differential mean QALYs between the two treatment groups will be estimated using multiple regression analysis. Specifically, a generalized linear model with appropriate link function (e.g., log-link) and response probability distribution (e.g., gamma distribution) will be used to analyze costs due to the potential skewness and heteroscedasticity of medical expenditure data, while an ordinary least squares regression will be used for analyzing QALY data. The models will account for treatment group, stratification factors, as well as other characteristics of the subjects that are found to differ significantly between the groups.[26] When estimating QALYs, we will also adjust for subjects' baseline utility scores to account for potential imbalance in baseline utility between the two treatment groups. [26] We will calculate the incremental cost-effectiveness ratio (ICER), which is the differential mean costs divided by the differential mean QALYs between the two groups, to assess the additional costs associated with each additional QALY gained. Our base case analysis will be conducted based on subjects with complete data. Sensitivity analysis will be conducted to include subjects with incomplete data using the multiple imputation method. Non-parametric bootstrapping resampling technique will be used to derive the 95% confidence interval for the ICER. In addition, cost-effectiveness acceptability curve (CEAC) will be generated to illustrate the likelihood that one treatment is more cost-effective than the other with various ceiling cost-effectiveness ratios. The cost-effectiveness evaluations will be conducted as within-trial comparisons. We plan to conduct supplemental analyses using other outcome measures including incremental cost per patient satisfaction.

14. Provisions to Monitor the Data to Ensure the Safety of Subjects

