Randomization assignment will be generated by computer based randomization table and assigned by a research coordinator not otherwise involved in the study. Assignments will be kept in sealed opaque envelopes numbered sequentially, and on the day of the patient's surgery, the surgeon will call a research coordinator who will open the next envelope in the sequence. This de-identified study subject number will then be assigned to the patient. All data collection sheets and questionnaires will contain the subject number and day of the hospital or clinic visit. No other patient identifiers will be collected. PHI including patient name, date of birth, phone number, medical record number will need to be collected to track for appointments.

The data collection, HIPAA and consent forms will be maintained in a locked file cabinet in the OBGYN administrative area. A separate folder will be designated for each participant. The offices have the additional security of being badge-access only for OBGYN department employees. A key matching study number to subject's name will be secured in a locked file cabinet in the OBGYN research administrative area.

The only PHI collected will be patient name, date of birth, medical record number and telephone number for site use only and to ensure patient follow up. This will not be entered into the database, but it will be kept with the other identifying information.

The data does not include sensitive information or information requiring additional protection.

All data will be kept in a locked file cabinet in the research administrative area. In order to further ensure patient confidentiality, the identifying information will be kept separately from the numbered study files in a locked cabinet.

Outpatient Visits versus Telephone Interviews for Postoperative Care: A Randomized Controlled Trial (OPTIONS)

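### Between-arm tests of PFDI-20 and pain are unadjusted unless the arms happen to differ at baseline, and extra cost and QALY covariates are chosen by significant imbalance; both should be fixed in advance

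*Combined protocol and SAP*

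**What the plan says.** Section 7.3 sets the exploratory aim: "determine if there is a difference in pain and pelvic floor symptoms in patients with follow-up with clinic visits versus telephone calls". Section 12 (Before Surgery) collects both instruments at baseline: "All patients will complete baseline questionnaires including the following: Surgical Pain Scales, Pelvic Floor Disorder Inventory (PFDI-20". They are repeated at the 3-month research visit in both arms.

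Section 13 makes the default methods unadjusted: Fisher's exact test, t-tests and, in the Power Analysis paragraph, "Wilcoxon Rank test for ordinal variables with significance set at" P<0.05. Adjustment is conditional in two places. The Data Analysis paragraph says "If there are any baseline differences between groups, and multivariate analysis will determine the contribution of these differences to observed differences". The Power Analysis paragraph says "Evaluation of potential confounders (e.g. age, baseline questionnaire) will be performed using regression methods, if, by chance there are differences between groups".

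For aim 3, the Statistical Analysis paragraph under Cost-Effectiveness Analysis says "The models will account for treatment group, stratification factors, as well as other characteristics of the subjects that are found to differ significantly" between the groups. For QALYs it also adjusts, without any condition, for "baseline utility scores to account for potential imbalance in baseline utility between the two treatment groups".

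Randomisation is described in sections 3.1, 12 and 16.1, for example "Randomization assignment will be generated by computer based randomization table and assigned by a research coordinator". None of the three mentions strata.

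**The concern.** After randomisation, baseline differences between arms are due to chance. What makes a covariate worth including is how well it predicts the outcome, not whether the arms happen to differ on it. A rule that waits for imbalance therefore selects on the wrong property and can leave out a strongly prognostic covariate because it is balanced.

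For PFDI-20 and pain, precision from data already in hand may be partly or wholly unused in the between-arm comparison. How much cannot be told, because the plan does not state the trigger, the score tested, or whether the adjusted or the unadjusted result leads. For aim 3, the additional terms in the cost and QALY models cannot be known until the data have been seen, and one named group of terms, the stratification factors, has no definition.

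**Working it through.** **The plan's own figure.** With 90% success in both arms, a 15-point margin, one-sided alpha 0.05 and 80% power, n per arm = (1.645 + 0.842)² × 2 × 0.9 × 0.1 / 0.15² ≈ 49.5, so 50 per arm and 100 in total. This matches section 5.3. It concerns only the primary outcome and does not depend on the point here. The plan gives no design figure for PFDI-20, pain, cost or QALY.

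**Inputs.** Women analysed: 120 × 0.9 × 0.9 = 97.2, taken as 49 v 48 (from the two 10% losses in section 13). The correlation r between baseline and 3-month score is not in the documents; assumed 0.3, 0.5, 0.7, with 0 and 0.1 as limits. An effect of 0.5 SD is also assumed.

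**Large-sample formulas.** The variance cut from ANCOVA is r² against a 3-month t-test (0.09, 0.25, 0.49) and (1 − r)/2 against a change score (0.35, 0.25, 0.15).

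**Simulation at 49 v 48.** Bivariate normal scores, 40,000 replicates per setting. The trigger is a t-test on the measure's own baseline; when triggered, ANCOVA replaces the default test.

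| Variance cut | r=0.3 | r=0.5 | r=0.7 |
|---|---|---|---|
| *Against 3-month t-test* | | | |
| ANCOVA always | 0.078 | 0.238 | 0.484 |
| Trigger p<0.05 | 0.020 | 0.065 | 0.133 |
| Trigger p<0.2 | 0.047 | 0.152 | 0.309 |
| Trigger p<0.5 | 0.072 | 0.220 | 0.447 |
| *Against change score* | | | |
| ANCOVA always | 0.346 | 0.244 | 0.141 |
| Trigger p<0.05 | 0.100 | 0.064 | 0.040 |
| Trigger p<0.2 | 0.230 | 0.156 | 0.093 |
| Trigger p<0.5 | 0.322 | 0.226 | 0.132 |

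Share of the gain recovered at r=0.5 against the t-test: 0.065/0.238 = 27%, 0.152/0.238 = 64%, 0.220/0.238 = 92%. The shares at the other correlations, and against the change score, are similar.

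Limits against the 3-month t-test: ANCOVA breaks even at r=0.1 (0.1% gain) and loses about 0.9% at r=0.

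Power for 0.5 SD at r=0.5: t-test 68%; triggered 69%, 71% and 75% at the three thresholds; ANCOVA 80%. At r=0.7: change score 88%, ANCOVA 92%. Type I error of the triggered rule at r=0.3 to 0.7 is 2.6% to 4.8%, so it is conservative, not inflated.

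**Aim 3.** A linear QALY-type model on arm and baseline utility (r=0.5 assumed), with one extra covariate of assumed partial correlation 0.1, 0.3 or 0.5, entered if the arms differ on it at P<0.05 (the only level the plan states); 20,000 replicates.

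- Always adjusting cuts variance by about 0%, 8% and 24%. The trigger cuts it by about 0%, 2% and 6%.
- When the covariate enters, the estimate moves on average 0.28, 0.68 and 1.16 standard errors. Mean estimates stay within 0.0013 of the true value of 0.
- Section 12 lists about 14 patient characteristics. The chance that at least one enters is 1 − 0.95^14 = 51% if the tests are independent at exactly 5%. It is 25–35% at true sizes of 2–3% (Fisher's test is conservative), and 1 − 0.95^5 = 23% if they act as five tests.
- The gamma cost model was not simulated.

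**The case against.** The strongest reply is that the plan may already use baseline. A reader might infer from section 13 that these scores ignore baseline unless the arms differ. The documents do not support that. If the default score is the change, baseline enters every analysis; and the planned within-group comparisons use it in any case. At r=0.7 an unadjusted change score already has 88% power against 92% for ANCOVA. This stands, so the point is confined to regression adjustment in the between-arm comparison.

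Second, the first statement of the trigger refers to *any* baseline difference. Two continuous means almost always differ, so read literally the rule comes close to always adjusting, and nearly all the gain is kept. This also stands as a possible reading, but it makes the plan's own condition empty, and the second statement still imposes one.

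Third, the second statement mentions a baseline questionnaire in a paragraph largely about S-CAHPS, so applying it to PFDI-20 and pain is partly inference. The first statement is general and carries the point.

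Fourth, r, the partial correlations and the effect size are assumed, surgery falls between the two measurements, and the simulation uses normal scores without the Wilcoxon option. That is fair; the ranges above are illustrations.

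Fifth, these are exploratory scores, and aim 3 already has its obvious covariate, baseline utility, fixed for QALYs. This limits the priority but does not justify choosing the remaining covariates by imbalance.

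**Conclusion.** The point holds as a low-cost improvement. Conditional adjustment for PFDI-20 and the Surgical Pain Scales is no better than always adjusting unless r is about 0.1 or less. For r between 0.3 and 0.7 the gain available is about 8–48% of variance against a 3-month t-test and about 34–14% against a change score. The unstated trigger decides whether roughly a quarter or nearly all of it is recovered.

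For aim 3, the selection rule is the wrong one and the stratification factors are undefined, but the gain from fixing covariates is small unless a clearly prognostic one exists beyond baseline utility. The documents identify none.

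A reader might infer inflated type I error, a biased ICER, or a threat to the primary result. None follows: the triggered rule is conservative, the simulated QALY-type estimates are unbiased, no bias in cost or ICER is shown, and the primary outcome and its sample size of 100 are unaffected. Priority is minor to moderate, since only exploratory and secondary outcomes are involved.

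**What to change.** 1. In section 13, make ANCOVA (3-month score on arm plus the same measure's own baseline) the lead between-arm analysis for PFDI-20 and each Surgical Pain Scale, whatever the baseline balance.
2. Keep the unconditional baseline-utility adjustment for QALYs.
3. Replace the imbalance triggers in the Data Analysis, Power Analysis and cost-effectiveness Statistical Analysis paragraphs with one short covariate list, chosen on prognostic grounds and named before the data are seen. Age, which the plan already mentions, is a candidate if the investigators judge it prognostic.
4. Delete the reference to stratification factors unless randomisation is stratified; if it is, name them in the randomisation text and in the models.

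The cost is a change of wording and one degree of freedom per covariate per model. No new data, visits or patients are needed. If baseline barely predicts the 3-month score, ANCOVA gains nothing over a 3-month t-test and loses about 1% of precision at worst.
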